Section 9.2.2.1 (No parallel section in Amendment 4.)	Not applicable.	
Header: Consultation with Medical Monitor and local hepatologist
 
Potential drug-induced liver injury events require notification of the Medical Monitor within 24 hours (eg, by laboratory alert), and the subject must be discussed with the Medical Monitor as soon as possible. If required, the subject must also be discussed with the local hepatologist. The local hepatologist is the expert usually consulted by the treating physician for assessment and management of potential hepatic disease. This would usually be a hepatologist, but may be a gastroenterologist. If determined necessary, this discussion should be followed by a full hepatology assessment (see Section 9.2.2.3) and SAE report (if applicable).
	Update to Sponsor template.

Section Impacted	Key components of previous text	Key components of amended text	Rationale
Section 9.2.2.2 (No parallel section in Amendment 4.)	Not applicable.	
Header: Immediate action: determination of IMP discontinuation
 
All PDILI events require immediate action, testing, and monitoring.
 
The immediate action is dependent on the laboratory values and symptoms of hepatitis or hypersensitivity and ranges from continuation of IMP (followed by immediate investigation) to immediate and permanent discontinuation (see Section 6.3.1 and Table 9-2 for details).
 
When IMP is discontinued, all concomitant medications and herbal supplements that are not medically necessary should also be discontinued. The Investigator should also consider dose reduction of medically necessary concomitant medication and consider changing any medically required concomitant medication known to be hepatotoxic to a suitable alternative.
	

Section Impacted	Key components of previous text	Key components of amended text	Rationale
Section 9.2.2.3 (No parallel section in Amendment 4.)	Not applicable.	
Header: Testing: identification/exclusion of alternative etiology
 
The measurements and additional information required for the assessment of PDILI events when there is a reasonable possibility that they may have been caused by the IMP are detailed in Table 9-3 (laboratory measurements) and Table 9-4 (additional information). Results of the laboratory measurements and information collected are to be submitted to the Sponsor on the corresponding eCRF. If the medical history of the subject indicates a requirement for other assessments not included below, these additional assessments should be completed and submitted, as applicable. All blood samples should be stored, if possible. If tests are done locally for more rapid results, a concurrent sample must also be sent to the central laboratory.
 
The following measurements are to be assessed:
 
Table 9-3: Added.
 
The following additional information is to be collected:
 
Table 9-4: Added.
	

Section Impacted	Key components of previous text	Key components of amended text	Rationale
Section 9.2.2.4 (No parallel section in Amendment 4)	Not applicable.	Header: Follow-up evaluation Potential drug-induced liver injury events will require follow-up monitoring as described in Table 9-2. Monitoring should continue until liver chemistry values normalize, stabilize, or return to baseline. Determination of stabilization is at the discretion of the Investigator in consultation with the hepatologist (as applicable) and UCB responsible physician, as needed.	Update to Sponsor template.
Section 9.2.3 (Section 9.5.2 of Amendment 4)	Not applicable.	Not applicable.	Update numbering.
Section 9.2.3.1 (Section 9.5.2.1 of Amendment 4)	Blood samples for the analysis of BRV will be collected at the FEV, YEV, FV, and at the EDV in the case of early discontinuation. A blood sample for determination of BRV plasma concentration should be taken whenever the subject experiences an SAE.	Blood samples for the analysis of BRV concentrations will be collected at the visits designated in Table 5-2. Additionally, a blood sample for determination of BRV plasma concentration should be taken whenever the subject experiences an SAE.	Remove information provided in Section 5.2 to decrease redundancy.
Section 9.2.3.2 (Section 9.5.2.2 of Amendment 4)	Subjects receiving phenytoin as a concomitant AED during the study will have blood samples collected at the ScrV (directly enrolled subjects only), FEV, YEV, FV, and at the EDV in the case of early discontinuation to monitor phenytoin plasma concentrations. Blood samples will only be collected at the SV if the plasma levels of phenytoin are abnormal at the EDV.	Subjects receiving phenytoin as a concomitant AED during the study will have blood samples collected at the visits designated in Table 5-1, Table 5-2, and Table 5-3 to monitor phenytoin plasma concentrations.	Remove information provided in Section 5.2 to decrease redundancy.
Section 9.3 (Section 9.6 of Amendment 4)	Not applicable.	Other safety measurements will be performed at the visits indicated in Table 5-1, Table 5-2, and Table 5-3.	Provide navigational text for reader.

Section Impacted	Key components of previous text	Key components of amended text	Rationale
Section 9.3.1 (Section 9.6.1 of Amendment 4)	A standard 12-lead ECG will be performed at the ScrV, TV(s), and EV (directly enrolled subjects only), YEV, FV, and at the EDV in the case of early discontinuation. An ECG will be performed at the SV only if the ECG results at the EDV are abnormal. At the EV, for LTFU subjects, ECG data will be obtained from the final visit of the previous pediatric BRV study and should not be recorded in the eCRF for N01266.	A standard 12-lead ECG will be performed.	Remove information provided in Section 5.2 to decrease redundancy.
Section 9.3.2 (Section 9.6.2 of Amendment 4)	Vital signs, including measurements of blood pressure, supine or sitting pulse rate, and body temperature, will be performed after 5 minutes of rest at the ScrV, TV(s), and EV (directly enrolled subjects only), MEV, FEV, YEV, FV, and at the EDV, DTV, and the SV in the case of early discontinuation. For LTFU subjects, at the EV, vital sign data will be obtained from the final visit of the previous pediatric BRV study and should not be recorded in the eCRF for N01266.	Vital signs, including measurements of blood pressure, supine or sitting pulse rate, and body temperature, will be performed after 5 minutes of rest.	Remove information provided in Section 5.2 to decrease redundancy.

Section Impacted	Key components of previous text	Key components of amended text	Rationale
Section 9.3.3 (Section 9.6.3 of Amendment 4)	
Header: Body weight and height
 
Body weight (subject wearing light clothing without shoes) will be measured at the ScrV, TV(s), and EV (directly enrolled subjects only), MEV, FEV, YEV, FV, and at the EDV and the SV in the case of early discontinuation. For LTFU subjects, at the EV, body weight will be obtained from the final visit and height data will be obtained from Baseline of the previous pediatric BRV study and should not be recorded in the eCRF for N01266.
 
Body height will be recorded at the ScrV (directly enrolled subjects only), MEV, FEV, YEV, FV, and at the EDV and the SV in the case of early discontinuation.
	
Header: Body weight, height, and head circumference
 
Body weight (subject wearing light clothing without shoes), height (length may be used for this measure, as appropriate), and head circumference (occipital-frontal circumference) will be measured.
	
Remove information provided in Section 5.2 to decrease redundancy.
 
Add information pertaining to the measurement of head circumference (in Amendment 4 this measurement was included in the neurological examination).

Section 9.3.4 (Section 9.6.4 in Amendment 4)	
A standard physical examination will be performed at the ScrV and EV (directly enrolled subjects only), FEV, YEV, FV, and at the EDV and the SV in the case of early discontinuation. For LTFU subjects, at the EV, physical examination data will be obtained from the final visit of the previous pediatric BRV study and should not be recorded in the eCRF for N01266.
	
A standard physical examination will be performed.
	
Remove information provided in Section 5.2 to decrease redundancy.

Section Impacted	Key components of previous text	Key components of amended text	Rationale
Section 9.3.5 (Section 9.6.5 of Amendment 4)	A standard neurological examination will be performed at the ScrV and EV (directly enrolled subjects only), FEV, YEV, FV, and at the EDV and the SV in the case of early discontinuation. For LTFU subjects, at the EV, neurological examination data will be obtained from the final visit of the previous pediatric BRV study and should not be recorded in the eCRF for N01266. The neurological examination will include a measurement of the head size (occipital-frontal circumference). Clinically significant new or worsened abnormalities must be reported as AEs.	A standard neurological examination will be performed. Clinically significant new or worsened abnormalities in the neurological examination must be reported as AEs.	Remove information provided in Section 5.2 to decrease redundancy. Remove head circumference from this section with inclusion in Section 9.3.3.
Section 9.3.6 (Section 9.6.6 of Amendment 4)	Psychiatric and mental status will be reported by recording the presence or absence of psychiatric symptoms, mental impairment, and behavioral problems at the ScrV and EV (directly enrolled subjects only), FEV, YEV, FV, and at the EDV and the SV in the case of early discontinuation. For LTFU subjects, at the EV, psychiatric and mental status data will be obtained from the final visit of the previous pediatric BRV study and should not be recorded in the eCRF for N01266.	Psychiatric and mental status will be reported by recording the presence or absence of psychiatric symptoms, mental impairment, and behavioral problems.	Remove information provided in Section 5.2 to decrease redundancy.

Section Impacted	Key components of previous text	Key components of amended text	Rationale
Section 9.3.7 (Section 9.6.7 of Amendment 4)	Not applicable.	The C-SSRS is not validated for subjects <6 years of age and will not be used for this population. Subjects should be monitored for any changes in mood, ideas, or behavior for warning signs of depression. The Investigator should be aware of common warning signs that might be a signal for risk of depression. For common signs and symptoms of depression in children younger than 6 years old, reference should be made to the current version of the Diagnostic and Statistical Manual of Mental Disorders. Parents and caregivers should also be advised accordingly and effort should be made at clinic visits to specifically assess potential depression.	Update to Sponsor template.
Section 9.3.8 (Section 9.6.8 of Amendment 4)	
The BRIEF-P/BRIEF will be completed at the ScrV (directly enrolled subjects only), FEV, YEV, FV, and the EDV in the case of early discontinuation. For LTFU subjects, at the EV, the BRIEF-P/BRIEF score will be obtained from Baseline of the previous pediatric BRV study and should not be recorded in the eCRF for N01266. For directly enrolled subjects, the Baseline BRIEF-P/BRIEF should be completed at the ScrV.
 
The BRIEF-P or BRIEF appropriate for each subject's age should be completed, with the following exception: For subjects who completed the BRIEF-P at the Baseline assessment and turn 5 years of age between that assessment and the initial YEV, the BRIEF-P should be completed through and including the initial YEV, and subsequently the BRIEF should be completed.
	Deleted.	Remove information provided in Section 5.2 to decrease redundancy.

Section 10

Section Impacted	Key components of previous text	Key components of amended text	Rationale
Section 10	The EEG data will be reviewed by 3-month periods for the first 6 months and yearly thereafter.	The EEG data will be reviewed at 6 months and yearly thereafter.	Revise in accordance with EEG timing.
Section 10.2	
At the EV, seizure data based on an EEG of at least 24 hours of recording (including sleeping and awakening periods) for subjects <2 years of age and data on absence seizure count (based on an EEG of at least 1 hour of recording for subjects \geq2 years of age suffering from absences) will be obtained from the final visit of the previous pediatric BRVstudy and should not be recorded in the eCRF for N01266.
 
The EEGs will be performed according to the following specifications:
 
• For subjects \geq2 years of age on the day of the study visit and with typical absence seizures: an EEG of at least 1 hour of recording (including hyperventilation and intermittent photic stimulation) will be performed starting at V4 and at every 3-month visit for the first 6 months and then yearly thereafter. For subjects prematurely discontinuing from the study, an EEG of at least 1 hour of recording should also be performed at the EDV.• For subjects \geq1 month to <2 years of age on the day of the study visit: an EEG of at least	Deleted.	Remove information provided in Section 5.2 to decrease redundancy.

Section Impacted	Key components of previous text	Key components of amended text	Rationale
	24 hours of recording (including sleeping and awakening periods) will be performed every 3 months during the first 6 months of the study, then yearly thereafter, and at the FV or the EDV in the case of early discontinuation.		
Section 10.3	Not applicable.	Other assessments will be performed at the visits indicated in Table 5-1, Table 5-2, and Table 5-3.	Provide navigational text for reader.
Section 10.3.1.1	Concomitant medication information will be collected and recorded in the eCRF at the following visits: ScrV and TV(s) (directly enrolled subjects only), EV, MEV, FEV, YEV, UV, FV, and at the EDV, DTV, and the SV in the case of early discontinuation. For LTFU subjects, any ongoing medications (including AEDs and non-AEDs) at the time the subject completed the core study should not be recorded in the eCRF for N01266, unless there is a change regarding the administration of the medication.	Concomitant medication information will be collected and recorded. For LTFU subjects, any ongoing medications (including AEDs and non-AEDs) at the time the subject completed the core study should not be recorded in the eCRF for N01266, unless there is a change regarding the administration of the medication.	Remove information provided in Section 5.2 to decrease redundancy. Provide intradocument consistency for “core study” terminology.
Section 10.3.1.2	Medical procedures will be recorded at the following visits: ScrV and TV(s) (directly enrolled subjects only), EV, MEV, FEV, YEV, UV, FV, and at the EDV, DTV, and the SV in the case of early discontinuation.	Deleted.	Remove information provided in Section 5.2 to decrease redundancy.

Section Impacted	Key components of previous text	Key components of amended text	Rationale
Section 10.3.1.3	
At the TV(s) and EV (directly enrolled subjects only), MEV, FEV, YEV, UV, FV, and at the EDV, DTV, and the SV in the case of early discontinuation, health care provider consultations not foreseen by the protocol will be recorded in the eCRF.
 
For LTFU subjects, at the EV, information on the health care provider consultations not foreseen by the protocol will be obtained from the final visit of the previous pediatric BRV study and should not be recorded in the eCRF for N01266.
	
Data collected for health care provider consultations not foreseen by the protocol will include the type of provider (general practitioner, specialist physician, nurse), the site of care (office-private, office-hospital, home, emergency room), and the reason leading to the consultation.
	Remove information provided in Section 5.2 to decrease redundancy.
Section 10.3.1.4	
During the TV(s) and EV (directly enrolled subjects only, MEV, FEV, YEV, UV, FV, and at the EDV, DTV, and the SV in the case of early discontinuation, data on hospital stays will be collected in the eCRF. It will include the reason leading to the hospitalization, the admission ward, transfers, and length of stay.
 
For LTFU subjects, at the EV, information on hospital stays will be obtained from the final visit of the previous pediatric BRV study and should not be recorded in the eCRF for N01266.
	
Data collected for hospital stays will include the reason leading to the hospitalization, the admission ward, transfers, and length of stay.
	Remove information provided in Section 5.2 to decrease redundancy.
Section 10.3.2	
The Bayley-III scales are recognized internationally as one of the most comprehensive developmental assessment instruments (Sattler and Hoge, 2006) used to examine the major facets of a young child's development (Bayley, 2006).
 
This scale is validated as a tool for assessment of neurological development in young children and is therefore considered appropriate for
	
The Bayley-III scales are validated as a tool for assessment of neurological development in young children and recognized internationally as one of the most comprehensive developmental assessment instruments (Sattler and Hoge, 2006) used to examine the major facets of a young child's development (Bayley, 2006).
 
Children started on the Bayley-III scales at Baseline of the core study will also be assessed
	
Remove information provided in Section 5.2 to decrease redundancy.
 
Remove information provided in Section 5.2 to decrease

Section Impacted	Key components of previous text	Key components of amended text	Rationale
	
N01266. The same scale has been completed by the Investigator or designee at Baseline (V1) of N01263 for children from 1 month to <18 months of age at Baseline enrolled in English-speaking countries. Children started on the Bayley-III scales at Baseline of N01263 will also be assessed using the Bayley-III scales in N01266 even if their age increases to ≥ 18 months. Bayley-III scale assessments are not applicable to directly enrolled subjects due to age-based considerations.
 
At the EV, the Bayley-III scales will be obtained from Baseline of the previous pediatric BRV study if the subject was enrolled in an English-speaking country, and data should not be recorded in the eCRF in N01266. The Bayley-III scales will be completed at the FEV, YEV, FV, and at the EDV in the case of early discontinuation. The Bayley-III scales should be completed by the same person who completed the Bayley-III scales in the previous pediatric BRV study.
 
At the EV, the Bayley-III scales will be obtained from Baseline of the previous pediatric BRV study if the subject was enrolled in an English-speaking country, and data should not be recorded in the eCRF in N01266. The Bayley-III scales will be completed at the FEV, YEV, FV, and at the EDV in the case of early discontinuation. The Bayley-III scales should be completed by the same person who completed the Bayley-III scales in the previous pediatric
	
using the Bayley-III scales in N01266 (if possible, by the same person who completed the scales in the core study) even if their age increases to ≥ 18 months. Bayley-III scale assessments are not applicable to directly enrolled subjects due to age-based considerations.
 
The Bayley-III scales will be applied to subjects as described in Table 5-1 and Table 5-2. The Bayley-III scale is not applicable to directly enrolled subjects due the age of these subjects (≥ 4 years of age) at entry into N01266.
	
redundancy.
 
Provide intradocument consistency for “core study” terminology.

Section Impacted	Key components of previous text	Key components of amended text	Rationale
	BRV study.		
Section 10.3.3	
The Achenbach CBCL should be completed by the same parent(s)/legal representative(s) who completed the CBCL in the previous pediatric BRV study. The completion of the Achenbach CBCL will require approximately 45 minutes.
 
The Achenbach CBCL will be completed at the ScrV (directly enrolled subjects only), FEV, YEV, FV, and at the EDV in the case of early discontinuation. For LTFU subjects, at the EV, the Achenbach CBCL score will be obtained from Baseline of the previous pediatric BRV study and should not be recorded in the eCRF for N01266.
	
The Achenbach CBCL should be completed by the same parent(s)/legal representative(s) who completed the CBCL in the core study, when possible. The completion of the Achenbach CBCL will require approximately 45 minutes.
	
Provide intradocument consistency for “core study” terminology.
 
Remove information provided in Section 5.2 to decrease redundancy.
 
Clarify that CBCL is to be completed by same person if possible.

Section 10.3.5	
The PedsQL will be completed at the ScrV (directly enrolled subjects only), FEV, YEV, FV, and the EDV in the case of early discontinuation. For LTFU subjects, at the EV, the PedsQL score will be obtained from Baseline of the previous pediatric BRV study and will not be recorded in the eCRF in N01266. For directly enrolled subjects, the Baseline PedsQL will be completed at the ScrV.
	Deleted.	
Remove information provided in Section 5.2 to decrease redundancy.

Section 11

Section Impacted	Key components of previous text	Key components of amended text	Rationale
Section 11.2.1	Not applicable.	Photocopies and/or printouts of eCRFs are not considered acceptable source documents.	Update to Sponsor template.
Section 11.3.1	This study will be performed using remote data capture.	This study will be performed using electronic data capture.	Update to Sponsor template.
Section 11.5	The Investigator will also notify UCB should he/she relocate or move the study-related files to a location other than that specified in the Sponsor's study master file.	The Investigator will also notify UCB should he/she relocate or move the study-related files to a location other than that specified in the Sponsor's trial master file.	Update to Sponsor template.

Section 12

Section Impacted	Key components of previous text	Key components of amended text	Rationale
Section 12.2	Not applicable.	Analyses may also be summarized for direct enrollers, as well as by core study (eg, EP0065 and N01349).	Provide additional information about possible data summaries.
Section 12.5	The Achenbach CBCL, the Bayley-III scores (LTFU subjects only), BRIEF-P/BRIEF, PedsQL, and change from Baseline scores (previous BRV study for LTFU subjects and ScrV for directly enrolled subjects) will be analyzed in a descriptive manner.	The Achenbach CBCL, the Bayley-III scores (LTFU subjects only), BRIEF-P/BRIEF, PedsQL, and change from Baseline scores (core study for LTFU subjects and ScrV for directly enrolled subjects) will be analyzed in a descriptive manner.	Provide intradocument consistency for "core study" terminology.

Section Impacted	Key components of previous text	Key components of amended text	Rationale
Section 12.9	
The original number was based upon the assumption that 90% of the subjects having completed a previous pediatric study with BRV as adjunctive treatment in epilepsy will rollover into the present study. With Protocol Amendment 3, enrollment was expanded to include up to 100 directly enrolled subjects (≥ 4 years to < 17 years of age) with POS, thus increasing possible enrollment up to 600 subjects. With Protocol Amendment 4, the number of directly enrolled subjects is increased to at least 100 subjects with the planned total enrollment of approximately 600 subjects.
	
The original number was based upon the assumption that 90% of the subjects having completed a core study will rollover into the present study. Planned enrollment now includes approximately 600 subjects, including at least 100 directly enrolled subjects, with no change in the assumption regarding core study completion.
	
Update to provide clarity regarding current design with no change to sample size.
 
Provide clarity regarding definition of “core study.”

Section 13

Section Impacted	Key components of previous text	Key components of amended text	Rationale

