Section 6.3.1 (No parallel section in Amendment 4)	Not applicable.	
Header: Potential drug-induced injury investigational medicinal product discontinuation criteria
 
Subjects with potential drug-induced liver injury (PDILI) must be assessed to determine if the investigational medicinal product (IMP) must be discontinued. In addition, all concomitant medications and herbal supplements that are not medically necessary should also be discontinued. The PDILI criteria below require immediate and permanent discontinuation of IMP:
 
 Subjects with either of the following: 
 ALT or AST ≥ 5xULN ALT or AST ≥ 3xULN and coexisting total bilirubin ≥ 2xULN 	Update to Sponsor template.

Section Impacted	Key components of previous text	Key components of amended text	Rationale
		
The PDILI criterion below requires immediate discontinuation of IMP:
 
Subjects with ALT or AST ≥ 3xULN who exhibit temporally associated symptoms of hepatitis or hypersensitivity. Hepatitis symptoms include fatigue, nausea, vomiting, right upper quadrant pain or tenderness. Hypersensitivity symptoms include fever (without clear alternative cause), rash, or eosinophilia (ie, $>5\%$). 
The PDILI criterion below allows for subjects to continue on IMP at the discretion of the Investigator.
 
Subjects with ALT or AST ≥ 3xULN (and ≥ 2x baseline) and <5xULN, total bilirubin <2xULN, and no eosinophilia (ie, $\leq 5\%$), with no fever, rash, or symptoms of hepatitis (eg, fatigue, nausea, vomiting, right upper quadrant pain or tenderness). 
Evaluation of PDILI must be initiated as described in Section 9.2.2. If subjects are unable to comply with the applicable monitoring schedule, IMP must be discontinued immediately. Investigators should attempt to obtain information on subjects in the case of IMP discontinuation to complete the final evaluation. Subjects with PDILI should not be withdrawn from the study until investigation and monitoring are complete. All results of these evaluations and observations, as well as the reason(s) for IMP discontinuation
	

Section Impacted	Key components of previous text	Key components of amended text	Rationale
		and subject withdrawal (if applicable), must be recorded in the source documents. The eCRF must document the primary reason for IMP discontinuation.	

Section 7

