		
by the treating physician for assessment and management of potential hepatic disease. This would usually be a hepatologist, but may be a gastroenterologist. Additional investigation and monitoring may be required and adapted based on the diagnosis after the cause of the liver injury/abnormality is confirmed (details in Section 9.2.2.4).
 
The results of all monitoring, including laboratory testing and other testing, should be made available to the study site and Sponsor.
 
All initial tests resulting in abnormal hepatic laboratory values need to be repeated, but appropriate medical action must not be delayed waiting for the repeat result.
 
If tests are done locally for more rapid results, a concurrent sample should also be sent to the central laboratory whenever possible. Medical care decisions are to be made initially using the most rapidly available results and a conservative approach must be taken if the results from the 2 laboratory tests are significantly different. Data from the local and central laboratory are to be recorded on the applicable eCRF pages.
 
When IMP is discontinued, all concomitant medications and herbal supplements that are not medically necessary should also be discontinued. In these cases, the Investigator should also consider dose reduction for medically necessary concomitant medication and consider changing any medically required concomitant medication known to be hepatotoxic to a suitable alternative.
 
Rechallenge with a substance potentially causing
	

Section Impacted	Key components of previous text	Key components of amended text	Rationale
		
drug-induced liver injury is dangerous, may be fatal, and must not occur.
 
The table below summarizes the approach to investigate PDILI.
 
Table 9-2: Added.
	

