		
safety assessment may need to be conducted, in a format that allows the Investigator to receive and review these results and include as source documentation.
 
Deviations to data collection including inability to perform some assessments such as EEG, ECG or blood collection for safety laboratory assessments and PK, or alternative methods of assessment such as phone calls should be recorded in the source documentation and notated as “not done” in the electronic case report form (eCRF).
 
In cases where subjects cannot return to the study site, and it will not be possible to dispense a new DRC, subjects will be instructed to continue recording of seizures in a manner that is mutually agreed with the Investigator (eg, hand-written notes, taking notes on a smart device). Any recording of seizures in a manner outside of the study DRC must be carefully documented in the source medical records (copies or printouts of these recordings will be brought to and retained at site).
	
Section 7.2.2	The maximum BRV dose will be 5.0mg/kg/day (2.5mg/kg bid), not to exceed a dose of 200mg/day for subjects with body weight >40kg.	The maximum BRV dose will be 5.0mg/kg/day (2.5mg/kg bid), not to exceed a dose of 200mg/day.	Removal of unnecessary text for clarification
Section 7.2.3	All subjects who prematurely discontinue the study should complete an EDV and have their BRV dose down titrated by a maximum of half the dose every week for a maximum of 4 weeks until a dose of 1mg/kg/day (50mg/day for subjects with body weights >50kg) is reached.	All subjects who prematurely discontinue the study should complete an EDV and have their BRV dose down titrated by a maximum of half the dose every week for a maximum of 4 weeks until a dose of 1mg/kg/day (50mg/day for subjects with body weights >50kg) is reached. Equally, all subjects completing the study but switching to treatment	To add down-titration information for subjects who do not continue BRV treatment after completing the study

Section impacted	Key components of previous text	Key components of amended text	Rationale
		other than BRV should have their BRV dose down titrated.	

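### Subjects who meet a PDILI stopping criterion have no single instruction: Section 6.3.1 stops IMP at once, while Sections 5.1, 7.2.3 and 7.7 supply drug and taper all early discontinuers without an exception

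*Protocol*

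**What the plan says.** Section 6.3.1, added by Amendment 5, has three tiers.

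- **Two laboratory criteria** (ALT or AST at or above 5xULN; or at or above 3xULN with total bilirubin at or above 2xULN): "The PDILI criteria below require immediate and permanent discontinuation of IMP".
- **Symptomatic tier** (ALT or AST at or above 3xULN with associated symptoms of hepatitis or hypersensitivity): "The PDILI criterion below requires immediate discontinuation of IMP". The word *permanent* is absent here.
- **Lowest tier** (at or above 3xULN but below 5xULN, bilirubin below 2xULN, no symptoms or eosinophilia): "The PDILI criterion below allows for subjects to continue on IMP at the discretion of the Investigator".

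The same section fixes an order of events: "Subjects with PDILI should not be withdrawn from the study until investigation and monitoring are complete". Section 9.2.2.2 repeats that the immediate action "ranges from continuation of IMP (followed by immediate investigation) to immediate and permanent discontinuation" and mentions no taper. On rechallenge with a suspect substance, Section 9.2.2 ends "drug-induced liver injury is dangerous, may be fatal, and must not occur".

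Section 7.2.3, in its Amendment 8 wording, reads "All subjects who prematurely discontinue the study should complete an EDV and have their BRV dose down titrated by a maximum of half the dose" each week, "for a maximum of 4 weeks until a dose of 1mg/kg/day" (50 mg/day above 50 kg) is reached. Section 5.1 gives the same taper after the EDV. Section 7.7 supplies IMP at the EDV in early discontinuation. Section 5.5, added by Amendment 8, provides down-titration instructions for a subject who has to be discontinued and cannot reach the site. None of these four sections, as shown, mentions PDILI.

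**The concern.** A site faced with a child who meets one of the stopping criteria finds two sets of instructions that cannot both be followed to the letter. One ends dosing now. The other attaches an EDV, a supply of drug and a stepwise dose reduction to leaving the study early, and covers everyone who does so. Neither refers to the other.

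The ordering in Section 6.3.1 adds a second difficulty. Withdrawal comes after the work-up, so the EDV and the drug supplied there would fall after IMP has already been stopped. Section 9.2.2 forbids renewed exposure to a substance that may have caused the injury.

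What is at stake is subject safety in a setting that the protocol itself calls potentially fatal, and whether sites handle the same event in the same way.

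**Working it through.** The plan states no figure to reproduce. The check sets the current texts side by side and adds one small dose calculation.

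**Step 1: are both sides current text?** Amendment 5 introduced Sections 6.3.1 and 7.2.3 together. Amendments 6 to 8, as shown, list no change to 6.3.1. Amendment 8 reworded 5.1, 7.2.3 and 7.7 and added 5.5, without a PDILI exception. The mismatch therefore lies between provisions in force, not between an amendment log and later text.

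**Step 2: can a subject in the two upper tiers follow everything?**

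| Course | Fits | Does not fit |
|---|---|---|
| Stop at once, no taper | 6.3.1, 9.2.2, 9.2.2.2 | 5.1, 7.2.3 and 7.7 as worded for all who leave early |
| Taper from the moment the criterion is met | The taper itself in 5.1 and 7.2.3 | *Immediate* in 6.3.1 |
| Stop, complete the work-up, then EDV with IMP and taper | The order in 6.3.1 and the letter of 7.2.3 and 7.7 | *Permanent* in 6.3.1 (two laboratory criteria only) and the rechallenge ban in 9.2.2 |

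No course satisfies every section as written. For the symptomatic tier, the third course conflicts only with the rechallenge ban, because 6.3.1 does not call that stop permanent. The lowest tier raises no conflict while IMP continues.

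**Step 3: how far apart are the readings?** Inputs: maximum dose 5.0 mg/kg/day, not above 200 mg/day (Section 7.2.2); weekly reduction of at most half; end dose 1 mg/kg/day, or 50 mg/day above 50 kg; at most 4 weeks (Section 7.2.3).

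- Fastest taper by weight: 5.0 → 2.5 → 1.25 → 1.0 mg/kg/day. The first two steps are halvings; the last is (1.25 − 1.0)/1.25 = 20%. That makes three reductions.
- Fastest taper above 50 kg from the cap: 200 → 100 → 50 mg/day, two reductions.
- Half is the largest step allowed, so smaller steps can fill the maximum: 4 × 7 = 28 days.

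Further BRV is 0 days if the subject stops without a taper and up to 28 days with one. In the third course, those days come after an interval off drug whose length depends on the work-up.

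**The case against.** **Different triggers.** Section 6.3.1 governs stopping IMP and Section 7.2.3 governs leaving the study. Section 6.3.1 keeps the two apart and treats withdrawal as something that may or may not apply. When IMP stops, the taper rule has not yet been triggered, and a subject already off drug has no current dose to reduce. This is the natural reading and it stands as such, but it is not written down. Section 7.2.3 covers all early discontinuers, and Section 7.7 has drug handed out at the EDV.

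**Specific and mandatory beats general.** The PDILI text requires and forbids, while 7.2.3 says only what should happen. That helps a careful reader, but Section 5.1 states the same taper as something subjects will have, so the verbs do not rank the rules cleanly.

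**Escalation.** Section 9.2.2.1 requires Medical Monitor notification within 24 hours and discussion as soon as possible, with the local hepatologist if required. This stands and lowers the risk considerably.

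**Variable taper length.** A schedule footnote in the reproduced Amendment 4 table makes the length of the Down-Titration Period depend on the final dose date. It varies the length and exempts nobody.

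**Unseen text.** Only part 2 of the protocol is shown, the change tables give key components, and Section 9.2.2.2 refers to Table 9-2 for details. An exception could stand there. This limits confidence.

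**Readings that go too far.** A reader might infer that the protocol orders BRV to be continued or restarted whenever liver injury is suspected. It does not: the stop is *permanent* for only two laboratory criteria, the lowest tier may stay on drug, and no sentence directs a restart. A reader might also cite the taper in the Amendment 4 liver rule, but that text is superseded and cannot show an error in the current plan.

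**Conclusion.** The point holds as an unreconciled instruction on subject safety, with moderate confidence. For the two upper PDILI tiers, the amended Sections 6.3.1 and 9.2.2 cannot be followed literally together with Sections 5.1, 7.2.3 and 7.7, and nothing shown settles which governs. The gap is 0 against at most 28 further days of BRV; 28 is a ceiling, because the fastest permitted taper needs only two or three reductions. The conclusion assumes that the consolidated sections match the change tables and that Table 9-2 contains no exception.

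A reader might infer a bias in the primary variables, treatment-emergent AEs and SAEs, through differing last-dose dates. The document does not support that. It shows no treatment-emergence window or exposure definition, which would normally sit in the SAP, and nothing shows that sites handled the matter differently. No view is taken on which clinical rule should prevail.

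**What to change.** Reconcile Sections 5.1, 5.5, 6.3.1, 7.2.3, 7.7 and 9.2.2 so that one instruction applies to each PDILI tier, with the same cross-reference in each section and agreement with Table 9-2. For a subject whose IMP is stopped under Section 6.3.1, state:

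- whether the general down-titration provision and the supply of IMP at the EDV apply;
- which of the EDV, DTV and SV the subject attends, and when, relative to the end of the liver work-up;
- which date is recorded as the last dose.

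The sponsor's medical team decides the content. The cost is an exception or cross-reference sentence in the next amendment and a letter to sites. It needs no change to the planned enrollment.
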